- 4) Subject has clinically significant (as determined by the investigator) renal, hepatic, hematologic, intestinal, endocrine, pulmonary, cardiovascular, neurological, psychiatric, immunologic, or other major uncontrolled diseases (e.g., malignancy, TB, HIV, HBV, HCV, thromboembolic events) that will affect the health of the subject during the study, or interfere with the interpretation of study results.
- 5) Subject has previously received treatment with oral or topical JAK inhibitors
- 6) Current other topical treatments (e.g., topical corticosteroids, topical calcineurin inhibitors) within 1 week of baseline
- 7) Use of systemic immunosuppressive medications, including, but not limited to, cyclosporine, systemic or intralesional corticosteroids, mycophenolate mofetil, azathioprine, methotrexate, tacrolimus within 4 weeks of study initiation
- 8) Concurrent use of strong CYP3A4 inhibitors within 7 days or 5 half-lives (whichever is longer). A list of CYP3A4 inhibiting medications can be found in Appendix 3.
- 9) History of adverse systemic or allergic reactions to any component of the study drug.
- 10) Current participation in any other study with an investigational medication
- 11) Subject who is pregnant or breast feeding

Inclusion Criteria For Control Subjects:

- 1) Male or female subjects \geq 18 years of age at the time of signing the informed consent document.
- 2) Subject is able to understand and voluntarily sign an informed consent document prior to participation in any study assessments or procedures.
- 3) Subject does not currently have and does not have a history of SD.
- 4) Female of childbearing potential (FCBP) must have a negative pregnancy test at Screening and Baseline

Exclusion Criteria For Control Subjects:

- 1) Active bacterial, fungal, or viral skin infection within 2 weeks from Screening/Baseline visit.
- 2) Subject has uncontrolled clinically significant (as determined by the investigator) renal, hepatic, hematologic, intestinal, endocrine, pulmonary, cardiovascular, neurological, psychiatric, immunologic, or other disease.
- 3) Subject has previously received treatment with oral or topical JAK inhibitors
- 4) Current other topical treatments (e.g., topical corticosteroids, topical calcineurin inhibitors) within 1 week of baseline

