- 5) Use of systemic immunosuppressive medications, including, but not limited to, cyclosporine, systemic or intralesional corticosteroids, mycophenolate mofetil, azathioprine, methotrexate, tacrolimus within 4 weeks of study initiation
- 6) Current participation in any other study with an investigational medication
- 7) Subject who is pregnant or breast feeding

POTENTIAL RISKS OF RUXOLITINIB 1.5% CREAM:

Based on phase 2 and phase 3 studies in atopic dermatitis, as well as phase 2 studies in vitiligo, topical application of ruxolitinib 1.5% cream shows a good safety profile. The most commonly experienced adverse events in the atopic dermatitis studies were application site burning and pruritus, which occurred more commonly in the vehicle control group (15). These results were mirrored in the phase 2 vitiligo study, with the additional observation of 18% of vitiligo patients experienced development of acne as a treatment-related adverse event (16). Although oral ruxolitinib has been associated with the risk of hematologic abnormalities in patients treated for polycythemia vera or myelofibrosis, pharmacokinetic analysis performed in the phase 3 studies in atopic dermatitis patients with up to 20% body surface area involvement demonstrated plasma ruxolitinib concentrations substantially lower than those required for systemic activity (17).

PRIOR TREATMENT:

All relevant treatment received by the subject within 30 days before screening will be recorded.

PROHIBITED TREATMENT:

Seborrheic Dermatitis Ruxolitinib Cream Protocol
Incyte IIR
March 25, 2022

All treatments prohibited during the screening period are also prohibited throughout the course of the study. All subjects treated previously with a topical or oral JAK inhibitor will be excluded from the study as above.

PROCEDURES:

Monitoring of Aes will begin at the time of signing the informed consent form and will be continued throughout the course of the study. All study procedures will be completed at designated times during the study period (see **Table 1**).

Trained assessors will perform clinical assessments. It is strongly recommended that the same assessor/s perform clinical assessments for a subject at all study visits.

For SD Subjects

Visit 1 – Screening (within 28 days of Baseline)*

- Obtain signed IRB-approved informed consent and HIPPA agreement
- Review Inclusion and Exclusion Criteria
- Record gender, race, ethnicity, and medical history

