The reasons why a subject may discontinue or be withdrawn from the study by the investigator include, but are not limited to the following: subject request, protocol violation, loss to follow up, subject non-compliance, defined as 4 missed applications during the 2 week period between study Visits, study termination by investigators, and a confirmed grade 3 or higher adverse event, which is suspected to be related to study drug administration. Subjects that elect to withdraw from the trial due to lack of efficacy and/or exacerbation of disease will undergo the following: vital signs; blood test; pregnancy test (if applicable); clinical photography; SD clinical assessments; DLQI questionnaire, assessment of concomitant medication and adverse events; blood collection for future mechanistic analysis; lesional tape strip collection.

Stopping Rules

Patients will be permanently discontinued from study treatment in the event of:

- Anaphylactic reaction or other severe systemic reaction to study drug application
- Pregnancy at anytime during the study period
- Diagnosis of a malignancy during study, excluding carcinoma in situ of the cervix, or squamous or basal cell carcinoma of the skin
- Any infection that is opportunistic, whose nature or course may suggest an immuno-compromised status
- Treatment with any prohibited concomitant medication or procedure
- Other reasons that may lead to the permanent discontinuation of study drug include certain Aes deemed related to the study drug.
- If the following lab results are abnormal, participants will be retested in a window of 7-10 days and reassessed. If the test results remain abnormal, participants will be discontinued from the study:

Hematology

Absolute Neutrophil Count: $<1000/\text{mm}^3$; $<1.0 \times 10^9/\text{L}$

Hemoglobin: $<8.0 \text{ g/dL}$; $<4.96 \text{ mmol/L}$; $<80 \text{ g/L}$

Hemoglobin drop $\geq 2 \text{ g/dL}$ from baseline on two consecutive blood draws with associated symptoms; or hemoglobin drop $\geq 3 \text{ g/dL}$ from baseline on two consecutive blood draws without associated symptoms.

Platelet count: $<75,000/\text{mm}^3$; $<75.0 \times 10^9/\text{L}$

Lymphocytes: $<500/\text{mm}^3$; $<0.5 \times 10^9/\text{L}$

Chemistry

AST $>3.0 \times \text{ULN}$

ALT $>3.0 \times \text{ULN}$

Total bilirubin $>1.5 \times \text{ULN}$

CPK $>10 \times \text{ULN}$

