Total bilirubin $\geq 1.5 \times \text{ULN}$; subjects with a history of Gilbert's syndrome may have a direct bilirubin measured and would be eligible for this study provided the direct bilirubin is $\leq \text{ULN}$

- Other intercurrent illnesses or major surgery
- An infection that requires systemic treatment with antibiotic, antifungal, antiviral, anti-parasitic, or anti-protozoal agents or requires oral treatment with such agents for longer than 2 weeks
- Treatment with systemic corticosteroids or non-steroidal immunosuppressive/immunomodulating medications (e.g., cyclosporine, methotrexate, azathioprine, mycophenolate-mofetil, Janus kinase inhibitors, biologic agents, etc.).

Safety Evaluation

Safety and tolerability will be evaluated from the Aes, physical examinations, and vital sign measurements. More frequent safety evaluations may be performed if clinically indicated or at the discretion of the investigator.

Aggregated Aes will be evaluated by the PI/research teams. The local IRB, FDA, and Incyte will be notified of adverse events.

The Principal Investigator (PI) must report all Serious Adverse Events (SAEs) to Incyte within 24 hours of learning of an event, regardless of the PI's causality assessment. This notification should be provided on a completed Serious Adverse Event (SAE) form. SAE reporting for each subject begins the day the informed consent is signed by the patient and within 14 days after subject has completed or discontinued from the study or has taken last dose of the study drug, or as described in the protocol.

SAEs, occurring using Incyte study drug, are reported in accordance with the effective protocol. SAEs occurring with any other commercial drug are reported to the manufacturer of that drug in accordance with regulations and protocol.

Initial SAEs and/or subsequent follow-up reports should be reported via email to [contact] or fax [name]. SAE reports should be for a single subject. SAE forms should be sent with a cover sheet and any additional attachments.

All adverse event information is reported to Incyte on the Principal Investigator's/Institution's Adverse Event Report Form, or a CIOMS-I or MedWatch Form FDA 3500A, or on an Adverse Event Report Form which may be provided by Incyte upon request. The Principal Investigator does not provide medical records (e.g., discharge summary) to Incyte, unless specifically requested.

Reporting of Pregnancy to Incyte

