Appendix 3 CYP3A4 Inhibitors.

CYP3A4 Inhibitors

Amiodarone	Indinavir
Amprenavir	Isavuconazole
Aprepitant	Itraconazole
Atazanavir	Ketoconazole
Boceprevir	Lopinavir
Casopitant	Mibepradil
Cimetidine	Mifepristone (RU486)
Ciprofloxacin	Nefazodone
Clarithromycin	Nelfinavir
Cobicistat	Netupitant
Conivaptan	Nilotinib
Crizotinib	Norfloxacin
Cyclosporine	Norfluoxetine
Danoprevir	Posaconazole
Darunavir	Ritonavir
Delavirdine	Saquinavir
Diltiazem	Schisandra sphenanthera
Dronedarone	Telaprevir
Elvitegravir	Telithromycin
Erythromycin	Tipranavir
Faldaprevir	Tofisopam
Fluconazole	Troleandomycin
Gestodene	Verapamil
Grapefruit Juice, marmalade	Viekira pak
Idelalisib	Voriconazole
Imatinib	

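### The laboratory stopping rules contradict each other on bilirubin in Gilbert's syndrome and set a CPK limit on a test that no scheduled visit names

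*Combined protocol and SAP*

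**What the plan says.** The list under Stopping Rules is mandatory: "Patients will be permanently discontinued from study treatment in the event of" any listed item. For laboratory limits, an abnormal result is retested after 7 to 10 days, and the patient is discontinued if it is still abnormal.

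- **Bilirubin.** The Chemistry limits contain two total bilirubin lines. One is above 1.5 times ULN, with no exception. The other is at or above 1.5 times ULN and adds that "subjects with a history of Gilbert's syndrome may have a direct bilirubin measured and would be eligible for this study", provided direct bilirubin does not exceed ULN.
- **CPK.** The same list gives a limit of more than 10 times ULN.
- **Laboratory schedule.** The SD visit lists name CBC with differential, a comprehensive metabolic panel (CMP), CRP and urinalysis at Baseline, Week 4 and Early Termination. Table 1 has no row for CPK or direct bilirubin. The contents of the CMP are not given.
- **CYP3A4 inhibitors.** Exclusion 8 for SD subjects is limited to strong inhibitors and refers to Appendix 3, which lists inhibitors without grading them and includes "Grapefruit Juice, marmalade". Under Prohibited Treatment, "All treatments prohibited during the screening period are also prohibited throughout the course of the study". The Stopping Rules then include "Treatment with any prohibited concomitant medication or procedure".
- **Infection.** Treatment stops where an infection "requires systemic treatment with antibiotic, antifungal, antiviral, anti-parasitic, or anti-protozoal agents or requires oral treatment with such agents for longer than 2 weeks". The word *systemic* is not defined.

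**The concern.** A mandatory stopping rule should give one answer for one patient and rest on a measurement that the schedule produces. The bilirubin lines fail the first requirement, and the CPK line, as scheduled, appears to fail the second. The CYP3A4 and infection wording leaves the scope of a permanent stop open.

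At stake is consistent handling. Two patients with the same results could be treated differently depending on which line is read. A limit meant as a safeguard may go unchecked because nobody is told to order the test. In a single-arm trial of 25 treated patients, each such decision also bears on who is still on drug at Week 4.

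**Working it through.** **The plan's own figures.** No calculated figure is in dispute. For completeness, the Sample Size Calculation reproduces. With n = 20 and success at 13 or more responders, P(X ≥ 13 | p = 0.40) = 0.0210 and P(X ≥ 13 | p = 0.75) = 0.898, against the stated 2.1% and 90%. Allowing for 20% dropout, 20 / (1 − 0.20) = 25. Nothing below changes these. The rest is a comparison of texts.

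**Bilirubin.** Apply each line to the same patient, with the value confirmed on retest and the Gilbert's exception read as applying to stopping:

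| Patient | Line with > 1.5 × ULN | Line with ≥ 1.5 × ULN | Agree? |
|---|---|---|---|
| Gilbert's, total 1.8 × ULN, direct ≤ ULN | discontinue | exempt | no |
| Gilbert's, total 1.8 × ULN, direct > ULN | discontinue | discontinue | yes |
| No Gilbert's, total 1.8 × ULN | discontinue | discontinue | yes |
| No Gilbert's, total exactly 1.5 × ULN | not met | discontinue | no |
| Gilbert's, total exactly 1.5 × ULN, direct ≤ ULN | not met | exempt | yes |

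The value 1.8 is only an example; any confirmed value above 1.5 gives the same first row.

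Reading the exception as an entry rule does not help. No inclusion or exclusion criterion mentions bilirubin (inclusion 7 refers only to laboratory testing in general), so there is no entry limit for it to modify. A patient let in under it would still meet a stopping limit once the value was confirmed.

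**Can the conflict arise on treatment?** Screening lists no blood draw. Chemistry is first drawn at Baseline, the visit at which drug is dispensed. Assume that the CMP reports total bilirubin and that the retest window runs from the draw:

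- Baseline (day 0): retest on days 7 to 10, before the Week 2 visit on day 14, so while the patient is on treatment.
- Week 4 (4 × 7 = day 28): retest on days 28 + 7 = 35 to 28 + 10 = 38, after remaining drug has been retrieved.

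The conflict can therefore affect treatment through a Baseline abnormality or an unscheduled draw, but not through a Week 4 result in a patient who completes treatment.

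**CPK.** Of the five scheduled SD visits and the Early Termination visit, none names CPK. Direct bilirubin, which the Gilbert's exception depends on, is not named either.

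**CYP3A4 scope.** Appendix 3 has 25 two-entry rows and one single entry: 25 × 2 + 1 = 51 entries, none graded. If the whole list is prohibited, use of any entry is a permanent stop. If only strong inhibitors are prohibited, the documents do not say which entries those are.

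**Infection rule.** If oral treatment counts as systemic, the first limb already covers every oral course and the 2-week limit does nothing. If it does not, an oral course of 2 weeks or less falls outside this rule. Appendix 3 also lists anti-infectives (ciprofloxacin, clarithromycin, erythromycin, fluconazole), so a short course of one of these may be a stop through the prohibited-medication rule whatever the infection rule means.

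**The case against.** **Any one limit suffices.** The chemistry limits are a list in which meeting one is enough. Read literally, a Gilbert's patient above 1.5 times ULN is stopped by the first line, and there is no conflict. That reading leaves the exception no effect on stopping except at exactly 1.5 times ULN, where the first line is not met. An express exception that a neighbouring line cancels still has to be reconciled. The retest requirement is also a fair point: a single high value stops nobody. Appendix 5 records both lines as added by Amendment #1, so the duplication is not an artefact of text extraction.

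**Stronger readings that a reader might infer, and why the documents do not support them:**

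- *The infection and CYP3A4 rules also give opposite answers.* They do not. The infection rule is one sentence with two limbs joined by *or*; failing the second limb does not say that treatment may continue. The CYP3A4 point is a mismatch of scope. To show two outcomes for a particular drug would need a potency grading that the documents do not give.
- *The CPK limit can never be triggered.* Safety Evaluation allows more frequent evaluations when clinically indicated or at the investigator's discretion, and the CMP contents are not listed. The supportable statement is that no scheduled visit names CPK.
- *Sites will apply the rules differently.* Study Design Overview places the trial at one institution. Inconsistency between patients or between reviewing investigators is possible; variation between sites is not.
- *Each unneeded stop uses up one of the five dropouts allowed for (25 − 20).* The list opens by stopping study treatment, whereas the laboratory item speaks of discontinuation from the study. The plan does not say whether a stopped patient has a Week 4 IGA or how that patient is scored.

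**Conclusion.** The concern holds as a defect in the laboratory stopping rules. The bilirubin lines conflict for a Gilbert's patient with a confirmed total above 1.5 times ULN and direct bilirubin no higher than ULN, and they differ at exactly 1.5 times ULN in a patient without Gilbert's. The CPK limit has no named scheduled test behind it. The CYP3A4 and infection points are secondary matters of wording.

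The size cannot be put as a number. The documents give no frequency for any of these cases and no scoring rule for stopped patients, so the effect on the primary endpoint cannot be quantified. The power and sample-size figures stand. The conclusion that the bilirubin conflict can arise on treatment assumes that the CMP reports total bilirubin. The CPK conclusion would change only if the CMP, as used here, includes CPK. The reason to act is that mandatory safety rules should be unambiguous and workable, and the correction is cheap.

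**What to change.** Reconcile the passages by amendment:

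1. Merge the two bilirubin lines into one and state whether the Gilbert's exception applies to entry, to stopping or to both. If it applies to entry, place it with a matching entry criterion. Say how direct bilirubin is to be obtained.
2. Make the CPK limit and the laboratory schedule agree, in the visit lists and in Table 1.
3. Make exclusion 8 and Appendix 3 agree in scope, so that it is clear which entries are prohibited and therefore lead to discontinuation.
4. Reword the infection rule so that its two limbs do not overlap.

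Which limit, exception or prohibition is clinically right is for the sponsor and investigator; this review takes no position.

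The cost is amendment wording and an edited appendix. If CPK testing is kept, it adds one analyte to blood already drawn. No change to sample size or to the primary analysis is needed.

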Ruxolitinib is an inhibitor JAK1 and JAK2 signaling, which suppresses the majority of the proposed SD-related cytokines simultaneously. In experimental models of dermatitis, ruxolitinib cream successfully reduced itch and down-regulated multiple inflammatory pathways (13). Although modulation of molecular biomarkers with application of ruxolitinib cream is lacking in humans, clinical efficacy has been shown in the Th2-driven disease atopic dermatitis in phase 2 (14) and phase 3 (15) studies, demonstrating the ability to normalize the pathogenic immune dysregulation in atopic dermatitis as well as in a phase 2 study of vitiligo (16), in which Th1 signaling is believed to play a major role. Furthermore topical approaches with immunomodulatory medications in SD [e.g., crisaborole (9)] have been used in small studies, supporting this approach.

Therefore, we hypothesize that topical ruxolitinib cream will be able to reverse the immune dysregulation seen in SD, leading to clinical improvement.

HYPOTHESIS:

Primary Hypothesis

- Twice daily application of ruxolitinib 1.5% cream for 4 weeks will be clinically efficacious in treating moderate-to-severe seborrheic dermatitis.

OBJECTIVES:

Primary Objectives

- To characterize the clinical responses to treatment with topical ruxolitinib 1.5% cream applied twice daily for 4 weeks in moderate-to-severe SD patients.

Secondary Objectives

- To characterize the molecular cutaneous phenotype of SD.
- To compare molecular biomarker expression in SD patients with healthy controls.
- To characterize the molecular responses to treatment with topical ruxolitinib 1.5% cream applied twice daily for 4 weeks in moderate-to-severe SD patients.
- To correlate the molecular and clinical responses to treatment with topical ruxolitinib 1.5% cream applied twice daily in order to identify biomarkers of treatment response in SD patients
- To validate a clinical SD disease severity score using assessments by two independent investigators
- To evaluate the safety and tolerability of topical ruxolitinib 1.5% cream applied twice daily for 4 weeks in moderate-to-severe SD patients

ENDPOINTS:

Primary Endpoint

- The proportion of patients who achieve an IGA 0/1 at 4 weeks of treatment with ruxolitinib 1.5% cream applied twice daily

Secondary Endpoints

- Change from baseline in IGA score at 4 weeks of treatment with ruxolitinib 1.5% cream applied twice daily

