An "Initial Pregnancy Report" or equivalent must be completed in full and emailed to [contact] or faxed to [name] within 24 hours of discovery of a pregnancy of a subject who has taken the Incyte product or the pregnancy of a partner for a subject who has taken the Incyte product. The "Follow-up Pregnancy Report Form" or equivalent must be completed and emailed to [contact] or faxed to [name] within 30 days after delivery, so that Incyte is provided with information regarding the outcome of the pregnancy. If the pregnancy results in any events which meet the serious criteria (i.e., miscarriage or termination), the SAE reporting process needs to be followed and the timelines associated with a SAE should be followed.

SUBJECT IDENTIFICATION

Subjects are numbered sequentially. Each subject will be assigned a unique screening number for the duration of the study. Subject screening numbers will not be reassigned or reused for any reason. The investigator must maintain a master log linking the subject number to the subject's name. The investigator must follow all applicable privacy laws in order to protect a subject's privacy and confidentiality.

STUDY DRUG SUPPLY:

Seborrheic Dermatitis Ruxolitinib Cream Protocol
Incyte IIR
March 25, 2022

Eligible patients will receive a supply of ruxolitinib 1.5% cream which they will apply to affected skin on the face only twice daily. Patients will be instructed not to use more than 60g of cream per week.

All study medication will be stored in a secure cool area between 15-30°C. Study drug will be provided to subjects at each study visit, with initial application performed at that time and subsequent applications performed by the patients at home.

Subjects will be queried during each study visit on any missed applications.

STATISTICAL CONSIDERATIONS:

Sample Size Calculation

A sample size of n=20 SD patients guarantees 90% power at 2.1% significance to detect a minimum proportion of 75% of patients with IGA 0/1 at week 4. This calculation assumes the application of the one-sided binomial test with a null hypothesis proportion of 40%. This proportion is based on the vehicle response benchmark reported by Zirwas et al.(2021) when comparing IGA 0/1 at week 8 in 154 patients treated with roflumilast foam 0.3% vs. 72 patients in the vehicle-controlled group(18). Accounting for a 20% dropout rate, we, therefore, propose a sample size of n=25 patients.

Mechanistic Endpoint

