To the best of our knowledge, this is the first study to evaluate differences in the transcriptome between SD and healthy subjects. A previous study (19) evaluated a fold-change (FCH) of 5 in IL-10 cell counts with coefficient of variation of 50% when comparing 10 SD subjects to 4 healthy volunteers. Assuming similar variability, a sample size of n = 20 SD subjects and n= 20 controls would provide 90% power at 5% significance to detect FCH>2.65 when comparing IL-10 expression between SD and controls, based on a two-sided unpaired t-test applied to log2-transformed RNA-seq data and fold-changes back transformed.

Demographics and Other Baseline Characteristics

Descriptive statistics of demographics and other baseline characteristics of patients will be summarized. Other baseline characteristics include height, weight, vital signs, duration of SD disease, concurrent diagnoses from medical history and indications for concomitant medication, concomitant medication, and previous SD treatments.

Analysis of Primary Endpoint

The one-sided binomial test will be used to verify the hypothesis that the proportion of patients achieving IGA 0/1 at 4 weeks of treatment with ruxolitinib 1.5% cream applied twice daily is greater than 0.4.

Analysis of Secondary Endpoints

The two-sided Wilcoxon signed-rank test will assess the significance of changes from baseline in:

- IGA score at 4 weeks of treatment
- Components of clinical SD scoring (scale, erythema, and pruritus) at 4 weeks of treatment.

The two-sided paired t-test will assess the significance of changes from baseline in:

- Overall clinical SD scoring at 4 and 6 weeks of treatment.
- Vital signs measured in interval or ratio scale
- Analytes measured in interval or ratio scale from laboratory tests (hematology, serum, chemistry, and urinalysis) at 4 weeks of treatment

The p-values will be adjusted by the Bonferroni method. The frequency, duration, and severity of AEs will be summarized with tables and summary statistics.

Analysis of Mechanistic (Exploratory) Endpoints

The baseline immune and molecular cutaneous profile of SD at baseline compared with healthy controls and the change in the immune and molecular cutaneous profile of SD with treatment will be assessed by MMRM approach. Gene/Protein expression data will be modeled using a mixed effect model with the interaction between tissue type (non-lesional/ lesional / healthy) and timepoint as fixed effects and a random effect for each subject.

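### The 40% null is a Week 8 vehicle rate from another product's trial, used as a known constant for a Week 4 single-arm endpoint; the 2.1% error holds against a fixed 40% but is not assured against Week 4 vehicle response

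*Combined protocol and SAP*

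**What the plan says.** The primary endpoint (Endpoints, Primary Endpoint) is "The proportion of patients who achieve an IGA 0/1 at 4 weeks of treatment with ruxolitinib 1.5% cream applied twice daily". Analysis of Primary Endpoint tests it against a constant: "The one-sided binomial test will be used to verify the hypothesis that the proportion of patients achieving IGA 0/1 at 4 weeks" exceeds 0.4. That section gives no significance level, no confidence interval and no alternative null.

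Statistical Considerations, Sample Size Calculation, states "A sample size of n=20 SD patients guarantees 90% power at 2.1% significance" against an alternative of 75% responders at Week 4, with a one-sided binomial test and a 40% null. On the origin of the 40% it says "This proportion is based on the vehicle response benchmark reported by" a trial of roflumilast foam, "when comparing IGA 0/1 at week 8 in 154 patients treated with roflumilast foam 0.3% vs. 72 patients in the vehicle-controlled group". It then says "Accounting for a 20% dropout rate, we, therefore, propose a sample size of n=25 patients".

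Study Design Overview describes an open-label trial in which every patient with seborrheic dermatitis receives the cream. The healthy controls have no IGA assessment in Table 1, so they cannot serve as a clinical comparator.

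**The concern.** In a single-arm trial the null value carries the whole comparison. Here it is presented as a vehicle response rate, but it differs from the tested endpoint in three ways.

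- **Time.** It is a Week 8 rate, and the endpoint is at Week 4. The documents give no Week 4 vehicle rate and no reason for carrying the later rate back.
- **Precision.** It comes from 72 patients and enters the test with no allowance for sampling error.
- **Setting.** It comes from a foam vehicle. This trial uses a cream on the face only (Study Drug Supply), in patients who have failed at least one earlier therapy (Inclusion Criteria For SD Subjects), with open-label rating. The plan does not say how the benchmark population compares.

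At stake is the meaning of a narrow success. A reader told that the null is a vehicle benchmark may take a positive test, with its 2.1% error rate, as evidence that the cream beats vehicle. With no interval or sensitivity analysis planned, nothing in the specified output would show how far that inference depends on the 40%.

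**Working it through.** **Inputs.** From Sample Size Calculation: n = 20 evaluable, null 0.40, alternative 0.75, one-sided exact binomial, 72 vehicle patients at Week 8, 20% dropout. Assumed: the vehicle responder count, which the documents do not give. 0.40 × 72 = 28.8, so I take 29/72 = 40.3%.

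**1. Reproduce the plan.** Let P(r, p) = Σ C(20,k) p^k (1−p)^(20−k), summed over k = r to 20.

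- P(13, 0.40) = 0.0210, the stated 2.1%.
- P(13, 0.75) = 0.898, which rounds to the stated 90%.
- Neighbouring cut-offs do not fit: 12/20 has error 5.65% and 14/20 has 0.65%.
- 20 / (1 − 0.20) = 25 enrolled.

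The implied rule is therefore at least 13 of 20, and the arithmetic is sound. It applies to 20 analysed patients. With all 25, at least 15 gives 3.4% and at least 16 gives 1.3%.

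**2. Uncertainty in the benchmark.** The exact (Clopper-Pearson) limits for x/n are the 0.025 quantile of Beta(x, n−x+1) and the 0.975 quantile of Beta(x+1, n−x). For 29/72 they are 28.9% and 52.5%. The Wilson interval is 29.7% to 51.8%. The Wald interval around exactly 40% is 0.40 ± 1.96 × √(0.40 × 0.60 / 72) = 28.7% to 51.3%. The choice of method matters little.

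**3. Chance of 13 or more of 20 if the drug does no better than vehicle,** by assumed true Week 4 vehicle rate. The same column is the one-sided p-value of an observed 13/20 against that null.

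| Vehicle rate | P(13, p) |
|---|---|
| 29% | 0.09% |
| 30% | 0.13% |
| 35% | 0.60% |
| 40% | 2.10% |
| 45% | 5.8% |
| 50% | 13.2% |
| 52.5% | 18.6% |

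Over the interval in step 2 the probability runs from about 0.1% to about 19%.

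**4. Average over the 72-patient sampling error.** With the vehicle rate distributed as Beta(29.5, 43.5), the beta-binomial probability of 13 or more of 20 is 3.9%. Using 28.8 in place of 29 gives 3.7%. This covers sampling error only, not differences in time point, vehicle or population.

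**5. What a just-successful result supports.** For 13/20 (65%) the exact two-sided 95% CI uses Beta(13, 8) and Beta(14, 7) and is 40.8% to 84.6%. Its lower part overlaps the benchmark's own interval of 29% to 53%.

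**6. Moving the null.** Against 30%, 11/20 would suffice (error 1.7%, power 98.6% at 75%). Against 50%, keeping error at or below 2.1% needs 15/20, and power at 75% falls to 61.7%.

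**The case against.** The plan tests whether the rate exceeds 0.4, and 2.1% is the right error for that hypothesis. The primary objective is to characterise clinical responses, and nowhere is superiority to vehicle promised. A fixed historical benchmark is usual in a small single-arm study. The time mismatch may well work against the sponsor: if vehicle response builds over time, the Week 4 rate is below 40% and the test is conservative. The higher error figures come from assumed vehicle rates of 45% and above, not from the mismatch. The average of 3.9% is below 5%, and success needs an observed 65%, above the upper limit of the benchmark interval. The 29/72 count is inferred from a figure the plan calls only a basis and may have rounded. Anyone given responders and n can compute an interval.

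Most of this stands. A reader might infer that the stated 2.1% is wrong, or that the design inflates false positives. The documents support neither: the figure is exact for the stated hypothesis, and no direction is shown for the mismatch. Nor do they support replacing 40% with a Week 4 rate. They do not show that the cited source reports one, and a lower null could drop the bar to 11/20 in an open-label trial.

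Two points survive. The plan itself describes the 40% as a vehicle benchmark without justifying it for Week 4, which invites the comparison. And the observed 65% has its own sampling error, with a lower limit of 41%, so clearing the benchmark's upper limit as a point estimate does not settle the question.

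**Conclusion.** The point holds as a minor one about justification and reporting. The 2.1% error and 90% power (exact: 2.10% and 89.8% with at least 13/20) are correct against a fixed 40%. They are not assured against true Week 4 vehicle response, because the 40% is a Week 8 estimate from 72 patients on another product's vehicle.

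If the benchmark was about 29/72, the chance of success for a drug no better than vehicle lies between about 0.1% and 19% and averages about 3.9%. These figures rest on the inferred count, on 20 analysed patients, and on sampling error alone. The Week 8 versus Week 4 difference could move the true error either way. The trial is not invalidated; what needs limiting is the conclusion that a borderline success can carry.

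**What to change.** Keep the test of at least 13/20 against 40%, and make three changes before the data are analysed.

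1. **Sample Size Calculation:** state that 40% is a fixed performance goal informed by a Week 8 vehicle rate, and that 2.1% and 90% refer to that goal.
2. **Analysis of Primary Endpoint:** add the exact two-sided 95% CI for the Week 4 response rate, and a prespecified sensitivity table of the exact one-sided test over nulls from about 30% to 50%. Include the Week 4 vehicle rate as one row if the cited source reports it.
3. **Conclusion:** word success as exceeding the fixed 40% goal, not as being better than vehicle.

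This needs a short text amendment and one small table, with no added patients, visits or samples. The downside is that a borderline success would be shown to depend on the benchmark: 13/20 has one-sided p = 0.021 against 40%, 0.058 against 45% and 0.13 against 50%.
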